2. INTRODUCTION

This statistical analysis plan (SAP) provides the detailed methodology for summary and statistical analyses of the data collected in Study A9001502. This document may modify the plans outlined in the protocol; however, any major modifications of the primary endpoint definition or its analysis will also be reflected in a protocol amendment.

Texts copied from the protocol are italicized.

2.1. Clinical Study Background

The overall objective of this study is to better understand why tumors become resistant to treatment with standard of care (SOC) therapies that target critical aspects of tumor biology. Limited availability of post-progression tumor tissue has compromised efforts to rigorously characterize the tumor genomic and microenvironmental factors that drive resistance. Understanding mechanisms of resistance is critical to developing better anti-cancer treatments and treatment combinations. This study specifically addresses the key challenges associated with studying clinical mechanisms of resistance.

Intrinsic or baseline tumor genetic heterogeneity, reflecting varying degrees of both intra- and inter-patient biologic diversity, represents a defining characteristic of cancer biology. In addition, the host response to cancer further defines the tumor microenvironment within which each patient's cancer is subject to further selection, establishing distinct immune landscapes that reflect the complex tumor-immune cell interactions. The introduction of targeted therapeutic agents that potently modulate tumor and/or immune cell biology impose additional, very specific, selection pressures that further define the evolving biology of each patient's cancer, frequently resulting in resistance following an initially beneficial treatment. Given the underlying genetic heterogeneity and the diversity of potential immune landscapes in cancer, informative analysis of mechanisms of resistance requires the application of robust platform technologies supporting immuno-genomic profiling of post-progression tumor tissue applied uniformly across a large series of patients.

Understanding clinical mechanisms of resistance has proven challenging because obtaining the required clinical tumor samples once resistance is established is difficult and the rationale for patients to undergo a de novo tumor biopsy after progression has been limited. As a result, studies of clinical mechanisms of resistance often derive at best from very limited number of studies or case reports, each describing results from analysis of small numbers of patients. Furthermore, these independent studies do not employ common or broad molecular profiling technologies, further limiting the utility of the information. This information gap compromises efforts to develop therapeutic agents or combinations of therapeutic agents that might overcome these mechanisms of resistance to initially effective anti-cancer therapies. Despite these limitations initial progress has been made in identification of clinical mechanisms of resistance to different therapeutic agents, and this has been complemented by studies of resistance in preclinical models, as summarized below. The development of high quality clinical Next Generation Sequencing (NGS) tests, together with the availability of a broad spectrum of targeted therapeutic agents that are approved or in clinical development, provides additional rationale to pursue a de novo tumor biopsy for patients in whom a biopsy procedure can be safely performed. Broad and deep genomic characterization by NGS in larger cohorts increases the probability of identifying clinically relevant resistance mechanisms.

2.2. Biomarker Study Design

This is a multi-national, multi-center study to collect and analyze archival pre-treatment tumor and post-progression biospecimens (de novo tumor biopsy and blood) from patients with advanced or metastatic cancer whose disease has progressed on selected SOC therapy. Evaluable patients are defined as those patients for whom paired archived and post-progression tumor tissue is sufficient for the planned translational analyses.

An initial pre-screening informed consent will be obtained to allow assessment of archival tumor tissue availability and adequacy. Only those patients who meet archival tumor tissue pre-screening requirements will be eligible to participate in the main study consisting of study-related procedures, post-biopsy follow-up visit and assessments. Molecular profiling, including NGS analysis, will be performed on the archival and post-progression biospecimens.

As part of study participation, results from the NGS analysis of the de novo post-progression biopsy and/or blood biospecimens will be returned to the patient's physician/health care provider. Results will come from tests performed in a College of American Pathologists (CAP) CAP-accredited, Clinical Laboratory Improvements Amendments (CLIA)-certified, and good clinical practice (GCP)-compliant clinical reference third-party laboratory using a commercially available NGS test. A study-specific follow-up consultation between the treating physician and patient will be conducted to discuss the NGS results and potential treatment options (see Schedule of Activities in the protocol). All treatment decisions, including potential referral to a clinical trial, will be per the treating physician as part of the patients' clinical care and are not dictated or defined by the study. Further details of the study design are described in Figure 1 and section 3 (Study Design) of the study protocol.

CCI

Target areas of biology, disease cohorts, prior SOC therapy, indications and cohort sizes are described in Table 1 and Section 3 (Study Design) of the study protocol. The total number of patients in this study depends on number of cohorts and cohort sizes. All cohorts will enroll concurrently. Individual cohorts and cohort sizes may be adjusted based upon emerging data. Cohort size refers to evaluable patients as defined above.

2.3. Biomarker Study Objectives

Table 1 Study Objectives

| |
|---|
| Primary Objective: |
| 
 • To obtain and analyze archival pre-treatment tumor samples and post-progression tumor biopsies to identify molecular markers of resistance to selected anti-cancer therapies. |
| Secondary Objectives: |
| 
 • To evaluate the success rate in obtaining paired archival and post-progression tumor biopsies that are adequate to meet the objectives of the study; • To determine concordance in gene alterations identified by NGS analysis of post-progression tumor tissue and blood. |
| Secondary Objectives by Target Biology:* |
| PD-1/-L1 inhibition: |
| 
 • To evaluate alterations in genes encoding HLA, β2-Microglobulin, Signal transducer and activator of transcription 1 (STAT1), JAK1, JAK2, IFN-γ, and interferon-gamma receptor (IFNGR) as mechanisms of resistance to PD-1/PD-L1 checkpoint blockade. |
| CDK4/6 inhibition: |
| 
 • To evaluate alterations in the Rb gene as a mechanism of resistance to palbociclib. |
| AR inhibition: |
| 
 • To evaluate AR gene alterations as mechanisms of resistance to enzalutamide or abiraterone; • To evaluate changes in expression of nuclear hormone receptor genes as a mechanism of resistance to enzalutamide or abiraterone. |
| PARP inhibition: |
| 
 • To evaluate somatic reversion of germline BRCA (gBRCA) gene alterations as a mechanism of resistance to monotherapy PARP inhibition. |
| CCI |
| |
| |
| |
| |

*All abbreviations are explained in the Appendix 1 of study protocol.

3. INTERIM ANALYSES, FINAL ANALYSES AND UNBLINDING

A formal interim analysis will not be performed for this study. However, multiple snapshots of the data will be taken for data review based on accrual (eg, at 25%, 50% and 75% of cohort and/or study accrual).

4. HYPOTHESES AND DECISION RULES

4.1. Biological and Statistical Hypotheses

No formal hypothesis testing will be performed.

4.2. Quantitative Decision Rules

Not applicable.

4.3. Operational Hypothesis

Not applicable.

5. ANALYSIS POPULATIONS

5.1. Safety Analysis (SA) Population

The SA population is defined as all patients who were enrolled and for whom a de novo biopsy procedure or research blood draw was performed.

5.2. Biomarker Evaluable Patient Analysis

The Biomarker Evaluable (BE) population is defined as patients in the SA population who have at least one biomarker result from analysis of collected biospecimen. The fully biomarker evaluable (FBE) population is defined as the patients in the SA population who have every biomarker result from analysis of collected biospecimen.

The Biomarker Evaluable Target (BET) population is defined as patients in the BE population who have a targeted tumor DNA panel biomarker result from both the archival and de novo biopsy tumor tissue biospecimen.

Additional subset populations include:

- BET (TTD), defined as all patients in the BET population who have results of targeted tumor DNA (TTD) NGS gene panel sample analysis from both the archival and de novo biopsy tumor tissue biospecimen.
- BET (TTR), defined as all patients in the BET population who have results of targeted tumor RNA (TTR) sample analysis from both the archival and de novo biopsy tumor tissue biospecimen.
- BET (WETD), defined as all patients in the BET population who have results of whole exome tumor DNA (WETD) NGS sample analysis from both the archival and de novo biopsy tumor tissue biospecimen.

- BET (WTTR), defined as all patients in the BET population who have results of whole transcriptome tumor RNA (WTTR) NGS sample analysis from both the archival and de novo biopsy tumor tissue biospecimen.

■ CCI

- BET (TTD-TTR), defined as all patients in the BET population who have both evaluable targeted tumor DNA (TTD) NGS gene panel data and targeted tumor RNA (TTR) sample analysis from both the archival and de novo biopsy tumor tissue biospecimen.
- BE (TBD), defined as all patients in the BE population who have results of targeted blood cfDNA (TBD) NGS gene panel sample analysis from the post- progression blood sample.
- BET (TBD), defined as all patients in the BET population who have results of targeted blood cfDNA (TBD) NGS gene panel sample analysis from the post- progression blood sample.

[figure not shown]

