5.3. Derivations and Excluded Data

All data will be included for statistical analysis except data resulting from sample analyses that fail QC Biomarker assays or tests from different bioanalytical laboratories and employing different platform technologies will have different QC standards and metrics that are defined as part of the assay or test validation. Exclusion of biomarker data for statistical analysis will reflect pre-defined QC criteria, established prior to final analyses, as reflected in bioanalytical reports from the bioanalytical laboratory.

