8.2.2. Analysis of Secondary Endpoints

Summary statistics will be generated for the secondary endpoints. For the proportion of patients with fully evaluable archival and post progression tumor biopsies, proportions and 95% CI will be calculated using the method described in [Section 8.1.2](#). For the overall agreement rates of gene mutations between post progression biopsy tissue and blood NGS results, basic summary statistics such as mean, median, and range of count of alterations per patient across all patients will be generated for each cohort. In addition, mean and median count of alterations in agreement between biopsy and blood samples will be calculated for each cohort. The frequency of alterations detected from post progression biopsy tissue, blood and the corresponding 95% CIs will be generated. In the BE (TBD) and BET (TBD) population, the concordance between both matched biopsy tissue and blood samples and the 95% CI and Cohen's Kappa will also be calculated to evaluate the agreement.

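### SAP 5.2 makes a paired panel-DNA result the entry condition for the exome and RNA pair sets, so QC-passing pairs can be dropped contrary to SAP 5.3, and SAP 8.2.2 does not say which of two sets leads for tissue-blood concordance

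*SAP*

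**What the plan says.** **Parent set.** SAP 5.2 defines BE as patients with at least one biomarker result. BET is the part of BE "who have a targeted tumor DNA panel biomarker result from both the archival and de novo biopsy tumor tissue biospecimen".

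**Sets nested in BET.** These include:
- "BET (TTD), defined as all patients in the BET population who have results of targeted tumor DNA (TTD) NGS gene panel sample analysis"
- "BET (WETD), defined as all patients in the BET population who have results of whole exome tumor DNA (WETD) NGS sample analysis"
- "BET (TTR), defined as all patients in the BET population who have results of targeted tumor RNA (TTR) sample analysis"
- "BET (WTTR), defined as all patients in the BET population who have results of whole transcriptome tumor RNA (WTTR) NGS sample analysis"

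Each of these four also requires the assay's result on both tissues. The matched blood set is "BET (TBD), defined as all patients in the BET population who have results of targeted blood cfDNA (TBD) NGS gene panel sample analysis". BE (TBD) is the same blood condition applied to BE, with no tissue result required.

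**Use of the sets.** SAP 8.2.1 analyzes the primary endpoint in BET (TTD) and BET (WETD). SAP 8.2.2 states: "In the BE (TBD) and BET (TBD) population, the concordance between both matched biopsy tissue and blood samples" will be assessed with a 95% CI and kappa. SAP 8.2.3 places all asset-specific endpoints on BET (TTD) and BET (WETD).

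**Inclusion rule.** SAP 5.3 includes all data except results that fail QC, and notes that assays "employing different platform technologies will have different QC standards and metrics".

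**Protocol.** Protocol 8.1 puts every endpoint on one evaluable population: patients with sufficient archival and de novo tissue.

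**The concern.** An analysis set should ask for the specimens its endpoint compares. The exome and RNA comparisons need an exome or RNA pair. The concordance endpoint needs the de novo biopsy and the post-progression blood. SAP 5.2 adds a panel-DNA pair to the first group, and archival panel DNA to one of the two concordance sets.

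Three things are at stake. Usable pairs from patients who underwent a study biopsy may be left out, including from one of the two primary-endpoint sets. The SAP contradicts its own inclusion rule. And concordance can be reported on two sets, with no statement of which is the main result or what its denominator is.

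**Working it through.** **1. Set logic (SAP 5.2 against SAP 5.3).** BET = BE with archival and de novo panel results. BET (TTD) repeats that condition, so it equals BET. BET (WETD) = BET with an exome pair; BET (TTR) and BET (WTTR) = BET with the respective RNA pair.

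Take a patient whose exome pair passes QC but whose archival panel fails. SAP 5.3 removes the failed panel result only. SAP 5.2 also removes the exome pair. The two rules give different primary-endpoint data sets.

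As a check, list all 2^7 = 128 present/absent profiles of archival and de novo panel, exome and RNA (taken as one assay) results, plus cfDNA:

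| Profiles with | Count | Of these, in the SAP set |
|---|---|---|
| Exome pair | 32 | 8 in BET (WETD) |
| RNA pair | 32 | 8 in the nested RNA set |
| De novo panel + cfDNA | 32 | 32 in BE (TBD); 16 in BET (TBD) |
| cfDNA, i.e. BE (TBD) | 64 | 32 have no de novo panel result |

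These are logical possibilities, not expected shares of patients.

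**2. Reproducing the plan's figures.** The only precision figures are in Protocol Table 2. Let b be the number of pairs altered only after progression, c the number altered only before, and n the number of pairs. The Tango score interval is the set of D with |b - c - nD| / sqrt(n[2q + D(1 - D)]) < 1.96, where q is the constrained estimate of the smaller discordant probability. With c = 0 and b = n x difference, all nine rows reproduce to the whole percent. For example:
- n=100, b=20: 13.3 to 28.9 (stated 13, 29)
- n=75, b=15: 12.5 to 30.4 (stated 13, 30)
- n=50, b=10: 11.2 to 33.0 (stated 11, 33)

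So no stated figure is wrong.

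**3. Size of a possible loss.** The share of valid exome or RNA pairs without a panel pair is not given. Assume 0-30%, an observed change of 20% and c = 0. Widths are in percentage points, from unrounded limits:

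| Share lost | Kept of 100 | CI width | Kept of 50 | CI width |
|---|---|---|---|---|
| 0% | 100 | 15.5 | 50 | 21.8 |
| 5% | 95 | 15.9 | 48 | 22.5 |
| 10% | 90 | 16.4 | 45 | 23.3 |
| 20% | 80 | 17.3 | 40 | 25.3 |
| 30% | 70 | 18.5 | 35 | 27.8 |

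Counts are rounded to whole patients, so the 48-pair row uses b = 10. The added width is 0.4 to 3.0 points at n=100 and 0.7 to 6.0 points at n=50, the size of cohorts 5 and 6 in Protocol Table 1.

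**4. Concordance.** Every patient with de novo panel and cfDNA results is in BE (TBD), so a calculation on matched samples there loses nobody. In BET (TBD), at an assumed 80% concordance, the Wilson width goes from 15.5 points (n=100) to 18.5 (n=70).

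The denominator matters only if *matched* were ignored. If patients without tissue were counted as non-agreeing, 80% would read 0.80 x 0.95 = 76%, 0.80 x 0.90 = 72% or 0.80 x 0.80 = 64% with 5%, 10% or 20% lacking tissue (assumed).

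**5. Overall agreement.** Suppose agreement were pooled over the 595 tissue-panel genes (SAP 7.1), with 5 altered genes in each specimen (assumed). With no overlap, agreement is 585/595 = 98.3%, kappa -0.01 and positive agreement 0/5 = 0%. With 3 shared, it is 591/595 = 99.3%, kappa 0.60 and 3/5 = 60%. Over 100 shared genes (assumed), overall agreement is 90% and 96%.

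**The case against.** **Concordance.** A reader might infer that concordance is run on patients without tissue, or that usable biopsy-plasma pairs are lost from it altogether. The text does not support either. SAP 8.2.2 speaks of matched samples, and BE (TBD) contains every patient who has both. A reader might also infer that the tissue and blood frequencies come from different patients. The frequency sentence names no population, so that cannot be shown. What stands is an unstated denominator and no named main set.

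**Archival requirement.** Protocol 8.1 already asks for paired tissue for all endpoints, so BET (TBD) is not arbitrary; BE (TBD) is the departure. This stands, and it is why the documents need reconciling. But Protocol 8.1 asks for tissue sufficient for the intended analyses. It does not make a panel-DNA result the gate for exome or RNA.

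**RNA.** No visible analysis uses BET (TTR) or BET (WTTR), and SAP 8.2.3 places even AR expression on the DNA-defined sets. Any use may lie in redacted text. So the RNA exclusion is a defect of definition with no demonstrated effect on a visible endpoint.

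**Likelihood.** Archival adequacy is confirmed at screening (Protocol 4.1 and 5.1.3), and panel and exome are tests from the same vendor on the same tissue (SAP 7.1). Losses may be few. This stands, and it limits the severity.

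**Overall agreement.** A reader might infer that the plan rests on an uninformative agreement rate. SAP 8.2.2 also plans kappa and counts of alterations in agreement, which separate the two cases in step 5. It does not state that agreement is pooled over all 595 genes.

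**Conclusion.** The point holds and is minor. By definition, BET (WETD), (TTR) and (WTTR) exclude QC-passing pairs that lack a panel pair. This conflicts with SAP 5.3 and, for exome, affects a primary-endpoint set. For concordance, no named set is defined exactly as de novo tissue plus blood, and neither of the two named sets is given precedence.

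The number of pairs lost cannot be computed from the documents. The widening in step 3 rests on an assumed 5-30% loss, a 20% change and no discordant pairs in the opposite direction. Concordance in BE (TBD) loses no matched patients. Protocol 8.2 calls the comparison hypothesis-generating and SAP 4 sets no decision rules, so no decision threshold depends on this.

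**What to change.** 1. In SAP 5.2, define BET (WETD), (TTR) and (WTTR) from BE instead of BET, keeping the requirement of a result on both tissues. For the RNA change to reach AR expression, SAP 8.2.3 would also have to name an RNA set.
2. In SAP 5.2 and 8.2.2, name BE patients with a de novo TTD result and a TBD result as the main set for concordance and for the tissue and blood frequencies compared with it. Keep BET (TBD) as a sensitivity analysis.
3. Reconcile both changes with Protocol 8.1.
4. Optionally, report positive percent agreement relative to tissue and relative to blood, over genes covered by both assays, beside overall agreement, kappa and the planned counts. This is a useful addition, not the correction of an error.

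The cost is SAP wording and light programming. Sample size will differ by assay, which SAP 8.4 already plans to tabulate by population and cohort. Because the exome set serves the primary endpoint, the sponsor should decide whether the change is major enough to be reflected in a protocol amendment (Protocol 8, SAP 2). Re-basing the exome and RNA sets can only keep or add usable pairs.

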5.3. Derivations and Excluded Data

All data will be included for statistical analysis except data resulting from sample analyses that fail QC Biomarker assays or tests from different bioanalytical laboratories and employing different platform technologies will have different QC standards and metrics that are defined as part of the assay or test validation. Exclusion of biomarker data for statistical analysis will reflect pre-defined QC criteria, established prior to final analyses, as reflected in bioanalytical reports from the bioanalytical laboratory.

6. ENDPOINTS AND COVARIATES

6.1. Endpoints

Table 2 Primary, Secondary and Exploratory Endpoints

| |
|--|
| Primary Endpoint: |
| 
 Change in the frequency of gene alterations between pre-treatment tumor samples and post-progression tumor biopsies. |
| Secondary Endpoints: |
| 
 Proportion of patients with fully evaluable archival and post-progression tumor biopsy (eg, sample sufficient for all intended analyses at all measured time points); Overall agreement rates of gene alterations between post-progression biopsy tissue and blood NGS results. |
| Secondary Endpoints by Target Biology:* |
| PD-1/L1 inhibition: |
| 
 Change in the frequency of alterations in genes encoding HLA, β2-Microglobulin, STAT1, JAK1, JAK2, IFN-γ and IFN-γR between pre-treatment archival and post-progression samples; The frequency of alterations in genes encoding HLA, β2-Microglobulin, STAT1, JAK1, JAK2, IFN-γ and IFNGR in cfDNA. |
| CDK4/6 inhibition: |
| 
 Change in the frequency of RB1 gene alterations between pre-treatment archival and post-progression samples. The frequency of RB1 gene alterations in cfDNA and tumor tissue. |
| AR inhibition: |
| 
 Change in the frequency of AR gene alterations between pre-treatment archival and post-progression samples; The frequency of AR gene alterations in cfDNA and tumor tissue; Changes in the expression of nuclear hormone receptors or related RNA signatures reflecting nuclear receptor pathway activity between pre-treatment archival and post-progression samples. |
| PARP inhibition: |
| 
 Change in the frequency of somatic reversion alterations in gBRCA mutant allele between pre-treatment archival and post-progression samples. |
| CCI |
|  |

*All abbreviations are explained in the Appendix 1 of study protocol.

6.2. Clinical Data Included in the Analysis

No clinical data will be analysed as dependent variables in this study.

6.3. Covariates

Additional covariates may be considered if regression models are used, including for example age, gender, race, cancer related medical history, duration of most recent cancer treatment and stage of tumor.

7. DATA PREPARATION

7.1. Biomarker Sample Analysis

- Biomarkers measured in both archival tumor tissue and the de novo tumor biopsy may include, but may not be limited to, the following:
 - Targeted tumor DNA (TTD) NGS gene panel (Tempus xT; 595 gene panel);
 - Whole exome tumor DNA (WETD) NGS (Tempus Whole Exome Sequencing);
 - Targeted tumor RNA (TTR) panel (HTG 2560-transcript Oncology Biomarker Panel (OBP));
 - Whole transcriptome tumor RNA (WTTR) NGS (Tempus RNaseq);
- Biomarkers measured in blood may include, but may not be limited to, the following:
 - Targeted blood cfDNA (TBD) NGS gene panel (Guardant 360 and/or Guardant OMNI).

